8.10 Pregnancy Testing and Contraception

Patients who are WOCBP will have a serum pregnancy test performed within the 3 to 7 days prior to Cycle 1 Day 1 and a urine pregnancy test performed on Day 1 (pre-infusion) of all cycles and at EOT. Additional pregnancy testing may be performed according to institutional practice.

Patients who are WOCBP and male patients whose partners are WOCBP will be counseled on the importance of avoiding pregnancy during the study and must agree to the use of at least 1 highly effective method of contraception, in the opinion of the Investigator. WOCBP must use a highly effective method of contraception during the study and for at least 90 days after the last dose of study treatment. Male patients must use a condom and refrain from sperm donation during the study and for at least 30 days after the last dose of study treatment. All patients will be instructed to report any suspected pregnancies in themselves or their partner up to 90 days after the last infusion.

8.11 Physical Examinations

Complete physical examinations, including a review of all body systems, will be performed at the Screening Visit, Day 1 of all cycles, and the EOT as shown in the Schedule of Events. Clinically significant findings observed during physical examination will be reported as medical history (pretreatment) or AEs (post-treatment).

Confidential and Proprietary

8.12 Eastern Cooperative Oncology Group

All patients will be assessed at Cycle 1 Day 1 using the ECOG Performance Status Scale. An ECOG performance score of 0 to 1 is required for study entry but is not a criterion for retreatment or study treatment discontinuation.

Table 14: ECOG Performance Status Scale

ECOG Performance Status Scale		
Grade	Description	
0	Fully active, able to carry on all pre-disease performance without restriction	
1	Restricted in physically strenuous activity but ambulatory and able to carry out work of a light or sedentary nature, e.g., light housework, office work	
2	Ambulatory and capable of all self-care but unable to carry out any work activities; up and about more than 50% of waking hours	
3	Capable of only limited self-care; confined to bed or chair more than 50% of waking hours	
4	Completely disabled; cannot carry on any self-care; totally confined to bed or chair	
5	Dead	

ECOG = Eastern Cooperative Oncology Group

8.13 Pharmacokinetics

Blood samples for tarloxotinib and tarloxotinib-E plasma concentrations will be collected prior to and following tarloxotinib infusion on Cycle 1 Day 1 and Cycle 2 Day 1. Serum potassium samples will also be collected after the infusion. Refer to the Laboratory Manual for sample collections, processing, and shipping instructions. All blood samples may be collected within the 5 or 10 minutes (see Schedule of Events) prior to or following the protocol-specified time point. Samples that cannot be collected with the sample collections window should be collected as soon as practicable and the actual date/time of collection reported.

8.14 Tumor Tissue

All patients will have tumor tissue collected at baseline. Tumor tissue may come from archived samples or from a recent pretreatment biopsy. Formalin-fixed paraffin embedded blocks are preferred, but if FFPE tissue is not available patients must have 8 to 10 prepared slides available. Mutation status will be confirmed after enrollment; these results will not be used to determine eligibility.

Tumor samples obtained during screening may also be used to determine levels of the reductase, STEAP4, which is responsible for generating the unstable intermediate species from the prodrug tarloxotinib to the pharmacologically active tarloxotinib-E under hypoxic conditions. As a third priority, if there is enough material, the samples will be used to for a hypoxia gene signature, phosphor-EGFR, and detection of EGFR homodimers by proximity ligation assay.

In addition to the above-mentioned tumor sample, an optional tumor tissue sample for measurement of the active metabolite (tarloxotinib-E) and tarloxotinib will collected from consenting patients on Cycle 1 Day 15 after infusion along with a blood sample for PK. If the

Confidential and Proprietary

biopsy (and associated PK sample) is not able to be performed on Cycle 1 Day 15, it should be collected within the 24 hours after the tarloxotinib infusion or after another infusion day.

Refer to the Laboratory Manual for samples collection, processing, and shipping instructions.

8.15 Biomarker Analysis

Blood samples will be collected for biomarker assessment (e.g., ctDNA) according to the Schedule of Events. Refer to the Laboratory Manual for samples collection, processing, and shipping instructions.

Biomarker assessment may include ctDNA mutation analysis and evaluation of the concordance of EGFR and HER2 mutation identification between blood and tumor tissue.

9. STATISTICS

The primary objective of this study is to evaluate the ORR of tarloxotinib according to RECIST v1.1.

ORR will be estimated with precision using the 95% exact binomial confidence interval (CI) limits. The analyses of time-to-event endpoints (DOR, PFS, and OS) will follow standard methodology by employing Kaplan-Meier and Cox proportional hazard model methodology.

Safety data will be summarized descriptively. AEs will be summarized by severity, seriousness, and relationship to study drug. Laboratory data will be compared to baseline values.

Additional exploratory data analyses will be conducted as appropriate.

Details of the statistical analyses presented below will be provided in the study's statistical analysis plan (SAP). A change to the data analysis methods described in the protocol will require a protocol amendment only if it alters a principal feature of the protocol. The SAP will be finalized prior to database lock. Any changes to the methods described in the plan will be described and justified in the final clinical study report.

9.1 Determination of Sample Size

The primary objective of this study is to determine if tarloxotinib provides a clinically significant tumor response to patients in each cohort. This will be investigated by assessing if the true ORR is at least above some desirable target level following therapy with tarloxotinib.

Currently approved EGFR or HER2 TKIs are, in general, ineffective against EGFR or HER2 exon 20 mutations and only associated with ORR of 12% or less (Robichaux 2018). Other treatment options for this population includes docetaxel, however, the ORR is no better than 15% (Hanna 2017).

For all cohorts, a Simon's 2-stage minimax design (Simon 1989) will be used. The null hypothesis that the true response rate is 15% will be tested against a one-sided alternative. In the first stage, 21 patients will be accrued. If there are 3 or fewer responses among these 21 patients, the cohort will be stopped. Otherwise, 22 additional patients may be accrued for a total of

Confidential and Proprietary

43 patients in each cohort. The null hypothesis will be rejected if 11 or more responses are observed in 43 patients. This design yields a type I error rate of 0.0454 and power of 0.8014 when the true response rate is 31%. The probability of early termination at the end of the first stage is 0.61 if the true response rate is 15% (Ivanova 2012).

9.2 Patient Disposition

9.2.1 Disposition of Patients

An accounting of the study patients will be tabulated. Patients not meeting the eligibility criteria will be identified. Patients not completing the study will be listed along with the reason for their premature discontinuation. Reasons for premature discontinuation will be summarized.

9.2.2 Protocol Deviations

Deviations from the protocol including violations of inclusion/exclusion criteria will be assessed as "minor" or "major" in cooperation with the Sponsor. Deviations will be defined prior to database lock. Handling of major deviations in statistical analyses will be defined in the SAP.

9.2.3 Analysis Sets

The primary efficacy analysis population includes all patients who received at least 1 dose of tarloxotinib. The Safety Population will consist of all patients who received at least 1 dose of tarloxotinib. The Safety Population will be the analysis population for the safety and primary efficacy analyses.

The Per Protocol (PP) Population is defined as patients who did not have a major protocol deviation that may affect interpretation of results. Efficacy will also be analyzed using the PP Population. A detailed specification of the PP Population will be provided prior to the database lock.

All enrolled patients who receive study treatment, have a baseline tumor assessment with documentation of measurable disease, have at least 1 on-study tumor assessment, whether or not this occurs at the specified imaging interval, and have no major protocol violations including inclusion/exclusion criteria or prohibited concomitant medication while on study, will be considered evaluable for response. Patients with a confirmed objective response (CR or PR) per RECIST criteria will be considered responders. Patients without a confirmed objective response, SD, or PD will be considered to be non-responders.

Patients who are treated and removed from the study prior to on-study tumor assessments because of clinical disease progression will be considered non-responders. Patients who are treated and removed from study prior to on-study tumor assessments for reasons other than clinical progression will be considered unevaluable for response and may be replaced. In addition, if a patient is enrolled without central laboratory confirmation of the specific gene alteration, and then is subsequently found not to have the specific gene alteration by central review, this patient will be considered unevaluable for response and may be replaced.

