D*	 Patients with advanced solid tumors who have failed all standard therapies appropriate for their tumor type and stage of disease, or, in the opinion of the Investigator, would be unlikely to tolerate or derive clinically meaningful benefit from appropriate standard-of-care therapy Patients with tumors (excluding NSCLC) harboring a HER2-activating mutation 	43
	Total	215

*Cohorts B1 and/or D may not be pursued, at the discretion of the Sponsor.

Patients who are not evaluable for tumor response assessment may be replaced; accordingly, the study is expected to enroll approximately 248 patients to yield 215 evaluable patients.

[figure not shown]
Prior to screening, potential patients will have tested positive for an EGFR exon 20 insertion mutation (Cohort A) or a HER2-activating mutation (Cohort B, B1, and D) or tumors harboring NRG1 or other HER-family gene fusions (Cohort C) using a CLIA-certified test (or similar accredited laboratory for non-US sites) to determine their eligibility for treatment with

Confidential and Proprietary

tarloxotinib. Results will be reviewed by the Medical Monitor (or designee) and participants will be assigned to one of the cohorts based on disease and mutation type.

Based on the determined recommended Phase 2 dose, all patients will receive tarloxotinib 150 mg/m² administered as a weekly 1-hour IV infusion on Days 1, 8, 15, and 22 of each 28-day cycle until disease progression or unacceptable toxicity (e.g., hepatotoxicity meeting Hy's law criteria or serious arrhythmias of ventricular origin). Radiographic tumor assessment including computed tomography (CT) scans or magnetic resonance imaging (MRI) of chest and abdomen will be performed every 8 weeks (± 5 days) from Cycle 1 Day 1, using the same imaging modality per patient (Section 7). Safety assessments will be performed on an ongoing basis.

Figure 12: Study Schema

EOT = End-of-Treatment Visit; FUP = Follow-up Visit

Note: This schematic is not to scale.

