9.3 General Considerations

Efficacy variables will be assessed without adjustment for multiple comparisons.

Confidential and Proprietary

Continuous data will be summarized by cohort using descriptive statistics (number of patients, number of missing information, mean, median, standard deviation, minimum, and maximum). Categorical data will be summarized by cohort using frequency tables (frequency counts and percentages).

The statistical test for primary efficacy endpoint ORR will be performed by cohort using an exact binomial test for single proportion at the 5% one-sided significance level, unless otherwise stated.

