9.6.1.2 Statistical Methods

The primary efficacy endpoint is confirmed ORR.

Objective response is defined as a CR or PR according to RECIST v1.1 recorded from baseline until disease progression or death due to any cause. Response assessment will be according to the local Investigator.

A patient will be considered to have achieved an objective response if the patient has a confirmed CR or PR according to RECIST v1.1. Additionally, patients with inadequate data for tumor assessment (e.g., no baseline assessment or no follow-up assessments) will be considered non-evaluable in the ORR analysis.

The ORR in each cohort will be estimated as the number of patients with confirmed objective response (CR or PR) divided by the number of evaluable patients in the respective cohort ("response rate"). The ORR will be summarized by cohort along with the corresponding 2-sided 95% CI. The best response rate will also be summarized similarly.

9.6.2 **Secondary Efficacy Analyses**

9.6.2.1 **Duration of Response**

The DOR is defined as the date of first documentation of OR according to RECIST v1.1 to date of disease progression or death to any cause. The DOR will be summarized using the Kaplan-Meier method and displayed graphically when appropriate. Median event times and the corresponding 2-sided 95% CI will be provided.

9.6.2.2 **Disease Control Rate**

The DCR is defined as CR, PR, or SD for at least 2 cycles (8 weeks) according to RECIST v1.1 recorded in the period between first study drug dose and disease progression or death to any cause.

The DCR for each cohort will be estimated by dividing the number of patients with CR, PR, or SD for at least 2 cycles (8 weeks) by the number of patients enrolled in each cohort. Similar analysis as for ORR will be performed for DCR.

9.6.2.3 **Progression-free Survival**

The PFS, which is defined as the time from the date of first tarloxotinib dose to the date of the first objective documentation of radiographic disease progression or death due to any cause, whichever occurs first. For the analysis, PFS data will be censored according to Table 15 for patients who are alive with no objective documentation of (radiographic) disease progression by the data cut-off date for PFS analysis.

Table 15: Censoring Rules for Progression-Free Survival

Situation	Date of Censoring
No baseline radiologic assessment	Date of first study drug dose

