## 9.2.10 Evaluable Subjects

A subject is classified as response evaluable if they have at least one response assessment or if they discontinue from treatment due to death prior to obtaining at least one response assessment. Subjects discontinuing treatment for disease progression must have a disease assessment performed documenting the progression

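### Protocol 9.2.3 and 9.6.1.2 give the primary ORR two denominators, all treated and evaluable-only with replacement; the evaluable-only one would bias ORR and both Simon decisions upward relative to all treated patients.

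*Protocol*

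**What the plan says.** **Protocol, all treated.** Section 9.2.3 defines the primary efficacy population as everyone given at least one dose and adds: "The Safety Population will be the analysis population for the safety and primary efficacy analyses". The synopsis says the same.

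**Protocol, evaluable only.** Later in Section 9.2.3, treated patients "removed from study prior to on-study tumor assessments for reasons other than clinical progression will be considered unevaluable for response and may be replaced". Those removed before a scan because of clinical progression count as non-responders. Patients with major violations, and those whose gene alteration is not found on central review, are also not evaluable. Section 9.6.1.2 gives the only ORR formula in the protocol: confirmed responders "divided by the number of evaluable patients in the respective cohort". It also calls patients without follow-up assessments non-evaluable, with no exception for clinical progression. Section 4.1 sizes the trial on the same basis: "the study is expected to enroll approximately 248 patients to yield 215 evaluable patients", which is 5 cohorts of 43.

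**Decision rule.** In Section 9.1, "The null hypothesis that the true response rate is 15% will be tested against a one-sided alternative". A cohort stops with 3 or fewer responses in 21 patients, and the null is rejected with 11 or more in 43. Section 9.3 specifies an "exact binomial test for single proportion at the 5% one-sided significance level".

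**Scans after stopping treatment.** Section 5.3 keeps patients who stop treatment for reasons other than RECIST progression on the scan schedule until progression, new anticancer therapy or discontinuation from the study.

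**SAP.** Section 4 says that the SAP governs where it differs from the protocol. Sections 8.2 and 15 use all treated subjects for ORR, and Section 9.1 drops efficacy testing. Section 9.2.11.1 divides ORR by enrolled subjects but cites Section 9.2.10, headed Evaluable Subjects, for the definition. Under 9.2.10 a subject with no response assessment is evaluable "if they discontinue from treatment due to death prior to obtaining at least one response assessment", and "Subjects discontinuing treatment for disease progression must have a disease assessment performed documenting the progression". Section 9.2.10.1 instead requires a baseline and at least one on-study tumor assessment. Enrolled subjects are actually defined in 9.2.1.2, as those who received a dose.

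**The concern.** A patient with no on-study scan cannot become a confirmed responder. If such patients leave the denominator and are replaced, the 21 and 43 places are filled with people who have already got as far as a scan, and the response rate in that group is higher than in all treated patients. Section 9.2.3 says that the population of interest is all treated patients, so a benchmark of 15% and a boundary of 11/43 would be met more easily than the stated error rate implies.

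Two features add to this. Replacement is optional in an open-label trial. And whether an early exit counts against the drug depends on whether the reason is recorded as clinical progression or as something else. Both matter for the Stage 1 decision to continue and for the final test.

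**Working it through.** **Inputs.** Null 15%, alternative 31%, stop at 3 or fewer of 21, reject at 11 or more of 43 (Protocol 9.1). Planned unevaluable share: 1 − 215/248 = 33/248 = 13.3% (Protocol 4.1).

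**Step 1: reproduce the stated design.** For a response rate p among the patients counted,

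- P(pass Stage 1) = P(Bin(21, p) ≥ 4)
- P(reject) = Σ over x = 4 to 21 of P(Bin(21, p) = x) × P(Bin(22, p) ≥ 11 − x)

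At p = 0.15, P(reject) = 0.0454 and early termination is 0.611. At p = 0.31, P(reject) = 0.8014. All three agree with Section 9.1, and the design is the minimax design for these inputs.

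**Step 2: effect of dropping and replacing.** Let d be the share of treated patients dropped as non-responders and replaced. If the all-treated ORR is 15%, the rate among those counted is p = 0.15/(1 − d).

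| d | p among those counted | P(pass Stage 1) | P(reject) |
|---|---|---|---|
| 0 | 15.0% | 0.389 | 0.045 |
| 3% | 15.5% | 0.412 | 0.055 |
| 5% | 15.8% | 0.429 | 0.062 |
| 6.7% (half the allowance) | 16.1% | 0.443 | 0.069 |
| 13.3% (whole allowance) | 17.3% | 0.505 | 0.104 |

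The documents do not split the 13.3% by reason, so the values of d below it are assumptions. The last row assigns the whole allowance to non-responding patients with no scan. Section 9.2.3 also puts major violations and unconfirmed alterations there, so that row is the upper case under the plan's own figure.

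**Step 3: at the boundary.** 11/43 = 25.6%. With 13.3% lost, 43 evaluable patients correspond to 43/(1 − 0.133) ≈ 50 treated, and 11/50 = 22.0%. The single-stage exact one-sided p-value against 15% is 0.049 for 11/43 and 0.120 for 11/50; 13/50 would be needed for p ≤ 0.05.

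**Step 4: cost of counting all treated patients.** If 31% describes all treated patients, power at 21 and 43 treated is 0.801, as stated. If 31% was meant for evaluable patients and 13.3% are lost, the all-treated rate is 0.31 × (1 − 0.133) = 26.9% and power is 0.61.

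**Step 5: the SAP reference.** The early-exit rules compare as follows.

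| Exit before any scan | Protocol 9.2.3 | SAP 9.2.10 | SAP 9.2.10.1 |
|---|---|---|---|
| Death not attributed to clinical progression | unevaluable | evaluable | not evaluable |
| Clinical progression | non-responder | scan documenting progression required | not evaluable |

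These differences reach the ORR only if a programmer follows the cross-reference in 9.2.11.1. The enrolled cohorts are 11, 22 and 8, so one subject would show: as an illustration only, 2/8 = 25.0% against 2/7 = 28.6%.

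**The case against.** The strongest reply is that nothing need be inflated. Section 9.2.3 names all treated patients as the primary population, and on that text the design figures hold. The SAP governs, reports ORR on all treated subjects and tests nothing. The trial ended early on a business decision with 41 subjects, so no cohort could reach 43. This stands: a reader might infer that the reported ORR is inflated, and the documents do not support that.

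A reader might also infer that every toxicity stop leaves the denominator. That is not supported either. The rule concerns removal from the study, Section 5.3 keeps patients who stop treatment on the scan schedule, and Section 9.2.3 accepts a scan at any time. A patient who stops for toxicity and is then scanned stays evaluable. Only those never scanned are lost, for example after death, withdrawal of consent or new therapy before a scan. Section 9.2.3 also keeps clinical progressors as non-responders, which limits the bias, although Section 9.6.1.2 states no such exception.

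Lastly, if the 15% null was meant for evaluable patients, type I error remains 0.0454. The protocol does not say which group it describes.

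What the reply does not remove is the conflict itself. The only ORR formula and the sample-size plan use evaluable counts, while the named primary population does not.

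**Conclusion.** The protocol gives the primary endpoint two incompatible denominators. If the evaluable and replacement text is followed, and 15% is the benchmark for all treated patients, the chance of a false positive is between 0.055 and 0.104 for 3% to 13.3% of treated patients dropped, against 0.045 as designed. The chance of passing Stage 1 rises from 0.39 to between 0.41 and 0.50. This rests on the dropped patients being non-responders. The 0.104 should not be read as the expected error rate, because it uses the whole allowance for one reason.

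The bias is therefore conditional, and it concerns the protocol's rules rather than the ORR that the SAP will report. In the SAP, what remains is the reference in 9.2.11.1 to the wrong definition and the disagreement between 9.2.10 and 9.2.10.1.

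**What to change.** **Protocol 9.2.3 and 9.6.1.2.** Use one denominator for the primary ORR and for the 21- and 43-patient decisions: all treated patients, with those who have no on-study scan counted as non-responders. Say that replacing a patient does not remove that patient from the denominator. Keep the evaluable-only ORR as a labelled sensitivity analysis.

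**Protocol 9.1.** State that 15% and 31% refer to all treated patients. If 31% was meant for evaluable patients, restate the power (about 0.61 with 13.3% lost) or revisit the sample size.

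**SAP.** Point 9.2.11.1 to Section 9.2.1.2, reconcile 9.2.10 with 9.2.10.1, and report the number of subjects with no on-study scan by reason for stopping.

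**Cost.** Wording changes and one table line; no new data. Under the protocol rule the ORR would be slightly lower, and the stated power may be lower or need more patients to keep. The SAP's ORR does not change, because it already uses all treated subjects.
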